8.11.7. Six-Minute Walk Test

The 6MWT is a well-established PerfO measure that is widely used to evaluate physical activity in terms of distance walked in patients with a variety of conditions. The test measures the distance an individual can walk on a hard, flat surface in 6 minutes and only requires a hallway that is ≥100 feet. The test is self-paced, and the individual can rest during the test as needed (ATS Committee on Proficiency Standards for Clinical Pulmonary Function Laboratories, 2002). In healthy adults, the normal range is from 400 to 700 meters (Enright, 2003). A lower score, based on less distance covered in 6 minutes, indicates worse level of physical activity.

9. ADVERSE EVENTS: DEFINITIONS AND PROCEDURES FOR RECORDING AND REPORTING

9.1. Definitions of Adverse Events

9.1.1. Definition of an Adverse Event

An AE is any untoward medical occurrence in a patient or clinical investigation subject administered a pharmaceutical product that does not necessarily have a causal relationship with this treatment. An AE can therefore be any of the following:

- Any unfavorable and unintended sign (eg, an abnormal laboratory finding), symptom, or disease temporally associated with the use of a study drug, whether or not considered related to the study drug.
- Any new disease or exacerbation of an existing disease (ie, a worsening in the character, frequency, or severity of a known condition)
- Recurrence of an intermittent medical condition (eg, headache) not present at baseline
- Any deterioration in a laboratory value or other clinical test (eg, ECG, x-ray) that is associated with clinical signs and symptoms, leads to a modification or discontinuation of study drug or concomitant therapy, requires medical or surgical intervention, or is considered by the Investigator to be clinically significant
- AEs that are related to a protocol-mandated intervention, including those that occur before assignment of study drug (eg, invasive screening procedures such as biopsies)

9.1.2. Definition of a Serious Adverse Event

An SAE is any AE or suspected adverse reaction that:

- Results in death
- Is immediately life-threatening
 - Life-threatening means that the subject was at immediate risk of death from the reaction as it occurred (ie, it does not include a reaction which hypothetically might have caused death had it occurred in a more severe form).
- Requires inpatient hospitalization or prolongation of existing hospitalization
 - Planned hospital admissions or surgical procedures for an illness or disease which existed before the subject was enrolled in the study or before study drug was administered are not to be considered AEs unless the condition deteriorated in an unexpected manner during the study (eg, surgery was performed earlier or later than planned).
- Results in persistent or significant incapacity or substantial disruption of the ability to conduct normal life functions
- Results in congenital anomaly/birth defect

- Is considered an important medical event
 - An important medical event is an event that may not result in death, be life-threatening, or require hospitalization but may be considered an SAE when, based upon appropriate medical judgment, it may jeopardize the subject or may require medical or surgical intervention to prevent one of the outcomes listed in the definitions for SAEs. Examples of such medical events include allergic bronchospasm requiring intensive treatment in an emergency room or at home, blood dyscrasias, or the development of drug dependency or drug abuse.

The terms "severe" and "serious" are not synonymous. Severity refers to the intensity of an AE (mild, moderate, or severe, or according to NCI CTCAE); the event itself may be of relatively minor medical significance (eg, severe headache without any further findings). Severity and seriousness need to be independently assessed for each AE recorded on the eCRF.

9.1.3. Abnormal Clinical Laboratory Events

A clinical laboratory test result should be reported as an AE if it meets any of the following criteria:

- Associated with clinical signs and symptoms
- Results in a dose modification or study drug discontinuation
- Requires medical or surgical intervention or a change in concomitant therapy
- Clinically significant in the Investigator's judgment

The Investigator is responsible for reviewing all clinical laboratory findings. Medical and scientific judgment should be exercised in deciding whether an isolated laboratory abnormality should be classified as an AE.

If a clinically significant laboratory abnormality is a sign or symptom of a disease or syndrome, only the diagnosis should be recorded on the AE eCRF.

If a clinically significant laboratory abnormality is not a sign or symptom of a disease or syndrome, the abnormality itself should be recorded on the AE eCRF, along with a descriptor indicating if the test result is above or below the normal range.

9.2. Procedures for Recording Adverse Events and Serious Adverse Events

9.2.1. Recording Adverse Events

Adverse events and SAEs that occur from the time of providing informed consent until 28 days after the administration of the last dose of study drug will be recorded on the appropriate pages of the eCRF.

Adverse events spontaneously reported by the subject and/or in response to open nonleading questions (eg, "How are you feeling?") from study personnel or revealed by observation,

physical examination, or other diagnostic procedures will be collected at every visit and recorded in the subject's medical record and in the appropriate pages of the eCRF.

Adverse events will be followed until 28 days after administration of the last dose of study drug or until study termination. Subjects will be assessed at the Safety Follow-up visit to determine if any new AEs have occurred. Adverse events that are ongoing at the time of study drug discontinuation should be followed through the Safety Follow-up visit. After this period, Investigators should report only SAEs that are considered related to study drug. Subjects who are withdrawn from the study due to a study drug-related SAE will continue to be followed until the SAE resolves or is declared chronic by the Investigator, or until the subject is lost to follow-up.

Any clinically significant deterioration in clinical laboratory test results (see Section 9.1.3) or other clinical finding that is considered an AE must be recorded in the eCRF. When possible, signs and symptoms indicating a common underlying pathology should be noted as one comprehensive event.

Information to be reported in the description of each AE includes:

- A medical diagnosis of the event (if a medical diagnosis cannot be determined, a description of each sign or symptom characterizing the event should be recorded)
- Event onset date
- Event resolution date
- Whether the event is serious (Section 9.1.2)
- Severity of the event (Section 9.2.2)
- Relationship of the event to study drug (Section 9.2.3)
- Action taken with study drug
- Event outcome

9.2.2. Severity of Adverse Events

The severity of all AEs, including clinically significant treatment emergent- clinical laboratory abnormalities, will be graded by the Investigator according to Version 4.03 of the NCI CTCAE on a 5-point severity scale (Grade 1 through Grade 5). Adverse events not specified by the NCI CTCAE will be graded according to Table 11.

Severity	Definition	NCI CTCAE
Mild	The event is noticeable to the subject but does not interfere with routine activity.	Grade 1
Moderate	The event interferes with routine activity but responds to symptomatic therapy or rest.	Grade 2
Severe	The event significantly limits the subject's ability to perform routine activities despite symptomatic therapy.	Grade 3

Table 11:Adverse Event Severity

Life-threatening	The subject was at risk of death at the time of the event.	Grade 4
Fatal	An event that results in the death	Grade 5

Abbreviations: NCI CTCAE = National Cancer Institute Common Terminology Criteria for Adverse Events.

An AE of severe intensity may not be considered serious. Severity is a measure of intensity, whereas seriousness is defined as described in Section 9.1.2.

9.2.3. Relationship to Study Drug

Investigators must determine whether an AE is considered to be related to the study drug, indicating "yes" or "no" according to the causal attribution guidance in Table 12.

Table 12:Causal Attribution Guidance

	Is the AE suspected to be caused by the study drug based on facts, evidence, science-based rationales, and clinical judgment?		
Yes	There is a plausible temporal relationship between the onset of the AE and administration of the study drug, and the AE cannot be readily explained by the subject's clinical state, intercurrent illness, or concomitant therapies; and/or the AE follows a known pattern of response to the study drug; and/or the AE abates or resolves upon discontinuation of the study drug or dose reduction and, if applicable, reappears upon rechallenge.		
No	Adverse events will be considered related unless evidence exists that the AE has an etiology other than the study drug (eg, preexisting medical condition, underlying disease, intercurrent illness, or concomitant therapy); and/or the AE has no plausible temporal relationship to study drug administration (eg, cancer diagnosed 2 days after first dose of study drug).		

Abbreviation: AE = adverse event.

When determining a causal attribution to study drug, the following guidance should be considered:

- Temporal relationship of event onset to the initiation of study drug
- Course of the event, considering especially the effects of dose reduction, study drug discontinuation, or study drug rechallenge, as applicable
- Known association of the event with the study drug or with similar treatments
- Known association of the event with the disease under study
- Presence of risk factors for the subject or use of concomitant therapies known to increase the occurrence of the event
- Presence of non-treatment-related factors that are known to be associated with the occurrence of the event

9.3. **Procedures for Reporting Adverse Events**

9.3.1. Reporting of Serious Adverse Events

All SAEs, regardless of relationship to study drug, that occur from the time of providing informed consent until 28 days after administration of the last dose of study drug must be reported to the Sponsor within 24 hours from the time when the Investigator becomes aware of

the SAE. This 24-hour notification applies to the initial SAE information and all follow-up SAE information.

Serious adverse events that occur more than 28 days after administration of the last dose of study drug that are considered by the Investigator to be related to study drug must be reported to the Sponsor any time the Investigator becomes aware of such an event.

The SAE eCRF must be completed and will include the following information: subject number, a narrative description of the event, and an assessment by the Investigator of the severity of the event and its relationship to study drug. Additional follow-up information on the SAE may be requested by the Sponsor or Medical Monitor.

If the electronic data capture (EDC) system is unavailable for more than 24 hours, SAEs must be reported using the EDC Downtime SAE Report Form. The SAE Report Form and completion instructions, a Safety Cover Letter, as well as a list of country-specific fax numbers are provided by the sponsor. Completed SAE reports may be submitted to Agios via email at [contact].

If there are suspected unexpected serious adverse reactions associated with the use of mitapivat, the Sponsor will notify the appropriate regulatory agency(ies) and all participating Investigators on an expedited basis. The local Institutional Review Board (IRB)/Independent Ethics Committee (IEC) will be promptly notified based on local regulations where required by the IRB/IEC of all serious, unexpected adverse drug reactions involving risk to human subjects.

Any on-treatment deaths, regardless of relationship to study drug, must be recorded on the appropriate eCRF and reported to the Sponsor within 24 hours. Deaths that occur during the protocol-specified SAE reporting period that are attributed by the Investigator solely to disease under study should not be reported as SAEs and should only be recorded on the End of Study eCRF page.

9.4. Other Safety-Related Issues

9.4.1. Overdose or Dose Administration Error

Overdose is the accidental or intentional use of the study drug in an amount higher than the dose being studied. An overdose or incorrect administration of study drug is not an AE unless it results in untoward medical effects. All AEs associated with an overdose or incorrect administration of study drug should be recorded on the AE eCRF. If the associated AE fulfills the criteria for an SAE, the event must be reported as specified in Section 9.3.1.

9.4.2. Pregnancy

Pregnancy is not reported as an AE unless there is a suspicion that an investigational product may have interfered with the effectiveness of a contraceptive medication or a complication relating to the pregnancy occurs that may qualify as an SAE (eg, spontaneous abortion). The Investigator must report any pregnancy that occurs during the treatment period and within 28 days after administration of the last dose of study drug, even in the absence of an AE. Pregnancy must be reported to the Sponsor within 24 hours of learning of its occurrence using a Pregnancy Report Form. Abnormal pregnancy outcomes (eg, maternal serious complications, spontaneous or therapeutic abortion, ectopic pregnancy, stillbirth, neonatal death, congenital anomaly, or birth defect) are considered SAEs and must be reported as specified in Section 9.3.1.

9.4.2.1. Pregnancy in Female Subjects

Female subjects who become pregnant while participating in the study will be immediately discontinued from study drug. Subjects should be encouraged to undergo the assessments at the Safety Follow-up visit. All AEs that occur during this time, including those related to the pregnancy, will be reported.

[figure not shown]
Investigators should counsel the subject regarding the risks of continuing the pregnancy and the possible effects on the fetus. The Investigator must follow-up and document the course and outcome of all pregnancies. Monitoring of the subject should continue until conclusion of the pregnancy. After completion of the pregnancy, attempts should be made to collect and report details of the outcome of the pregnancy and development of the child.

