- ¹ At any time during the study, subjects who discontinue study drug should undergo the recommended dose taper and complete the assessments at the Safety Follow-up visit after administration of their last dose of study drug (ie, including the recommended dose taper). Subjects who withdraw from the study should be encouraged to first undergo the recommended dose taper (Table 4) and complete the Safety Follow-up visit. Subjects who are discontinuing study drug should be monitored for signs of hemolysis and worsening of anemia, as clinically indicated.
- ² The Safety Follow-up visit is to be completed after administration of the last of any dose of study drug (ie, including the recommended dose taper).
- ³ If allowed by local institutional guidelines, and at the discretion of the Investigator and the subject, subjects will have the option to complete study-specific assessments at home instead of in person at the clinical study center. These visits (Investigator Assessment only) will be conducted by the Investigator (or designee) (see Section 8).
- ⁴ After completing the study visit at Week 288, subjects should begin the dose taper.
- ⁵ Pregnancy testing should occur more frequently as clinically indicated (ie, if there is suspicion of pregnancy) or if required by local regulations. A serum or urine pregnancy test will be performed locally for WOCBP at the Safety Follow-up visit.

Η

- ⁸ Vital signs include systolic and diastolic blood pressure, pulse rate, and body temperature. Weight will also be recorded. Vital signs should be measured after 5 minutes of recumbency, and before blood sample collection.
- ⁹ Hematology includes a complete blood count (Hb, HCT, MCHC, MCH, MCV, RBC count, nucleated RBCs, RDW-CV, % reticulocyte count, absolute reticulocyte count, and platelet count) with WBC count and differential (neutrophils, basophils, lymphocytes, and monocytes).
- ¹⁰Clinical chemistry includes albumin, BUN or urea, total calcium, CO₂ or bicarbonate, chloride, creatinine, magnesium, magnesium, phosphorus, potassium, sodium, total protein, and uric acid.
- ¹¹Liver tests include ALP, ALT/SGPT, AST/SGOT, and bilirubin (direct/conjugated, indirect/unconjugated, and total). LDH will also be measured.
- ¹²Lipid panel includes nonfasting HDL-C, LDL-C, total cholesterol, and triglycerides.

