6. STUDY DRUG

6.1. Study Drug Administered

Study drug is defined as mitapivat or matched placebo. Study drug is for investigational use only and to be used only within the context of this study protocol.

Subjects will receive 100 mg BID mitapivat or matched-placebo for oral administration. Tablets are to be swallowed whole with water and may be taken with or without food. Tablets are not to be crushed, chewed, or dissolved in water. If a dose of mitapivat is missed by \leq 4 hours, the dose should be taken as soon as possible. If a dose of mitapivat is missed by >4 hours, the dose should be skipped and taken at the time of the next scheduled dose. The regular dosing schedule should resume the following day.

Subjects who discontinue study drug should undergo the recommended dose taper and be monitored as clinically indicated for signs and symptoms of acute hemolysis and worsening anemia. If immediate or abrupt study drug discontinuation is required for an AE or medical emergency, subjects should be monitored as clinically indicated for signs of acute hemolysis or worsening anemia. Study drug dose modifications are provided in Section 6.7.

Study drug dose and recommended dose taper are provided in Table 4.

Level	Dose	Schedule
Full dose	100 mg	BID
Taper dose	100 mg	QD for 7 days, then discontinue study drug

 Table 4:
 Study Drug Dose and Recommended Dose Taper Regimen

Abbreviations: BID = twice daily; QD = once daily.

Study drug will be supplied according to the specifications in Table 5.

Table 5:Study Drug

Treatment Arm:	Active	Matched Placebo
Study drug name (INN)	Mitapivat (AG-348)	NA
Dose formulation	Tablet	Tablet
Tablet unit strength(s)	100 mg	NA
Appearance	Oblong blue tablet	Oblong blue tablet
Route of administration	Oral	Oral
Sourcing	Provided by the Sponsor	Provided by the Sponsor
Packaging and labeling	Provided in containers with child resistant closures and labeled as required per local regulations.	Provided in containers with child resistant closures and labeled as required per local regulations.

Abbreviations: INN = international nonproprietary name; NA = not applicable.

Additional information will be provided in the Pharmacy Manual.

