6.7. Dose Modifications

Dose modifications for excessive Hb response, study drug-related AEs and

are detailed in Section 6.7.1.1, Section 6.7.1.2, and Section 6.7.1.3. Dose modification decisions should be made by the Investigator based on a clinical evaluation of the subject. The Investigator should notify the Medical Monitor of any dose modifications that are planned or instituted.

Subjects who discontinue study drug should undergo the recommended dose taper (Table 4) and be monitored as clinically indicated for signs and symptoms of acute hemolysis and worsening anemia. If immediate or abrupt study drug discontinuation is required for an AE or medical emergency, subjects should be monitored as clinically indicated for signs of acute hemolysis or worsening anemia.

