6.7.1.2. Dose Modifications for Study Drug–Related Adverse Events

[figure not shown]
Dose modifications for study drug–related AEs, except for events of excessive Hb response , are provided in Table 7.

Table 7:Dose Modifications for Study Drug–Related Adverse Events Except for
Events of Excessive Hemoglobin Response

AE Severity ¹	Study Drug N	Study Drug Modification	
Grade 1 (mild)	None required	None required	
Grade 2 (moderate)	None required	None required	
Grade 3 (severe)	First occurrence	Reduce to 100 mg QD.	
		• If the event resolves to Grade ≤2 within 28 days of the dose reduction, increase to 100 mg BID.	
		• If the event does not resolve to Grade ≤2 within 28 days of the dose reduction, discontinue study drug.	
	Second occurrence	Reduce to 100 mg QD for 7 days, then discontinue study drug.	
Grade 4 (life-threatening)	Reduce to 100 mg QD for 7 days, then discontinue study drug.		

Abbreviations: BID = twice daily; QD = once daily.

¹ Adverse event severity assessed as mild, moderate, or severe, or according to National Cancer Institute Common Terminology Criteria for Adverse Events.

AG348-C-017

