7. STUDY DRUG DISCONTINUATION AND SUBJECT WITHDRAWAL FROM STUDY

7.1. Study Drug Discontinuation

In some instances, it may be necessary for a subject to discontinue study drug. Subjects may be discontinued from study drug for the following reasons:

- Completed
- Adverse event
- Death
- Lost to follow-up
- Physician decision
- Pregnancy
- Protocol deviation
- Study terminated by sponsor
- Withdrawal by subject
- Other

The primary reason for study drug discontinuation will be recorded in the eCRF. All efforts will be made to complete and report protocol-defined study observations as thoroughly as possible. Subjects who are discontinuing study drug should undergo the recommended dose taper and be monitored as clinically indicated for signs and symptoms of acute hemolysis and worsening anemia. Assessments to be completed at the time of study drug discontinuation are specified in the Schedules of Assessments (Table 2).

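### The protocol does not settle whether a subject who becomes pregnant stops study drug at once or takes the 7-day taper

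*Protocol*

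**What the plan says.** **Pregnancy.** Protocol Section 9.4.2.1 reads "Female subjects who become pregnant while participating in the study will be immediately discontinued from study drug". It then encourages the Safety Follow-up assessments. The taper is neither required nor excluded.

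**Stopping in general.** Section 7.1 lists the reasons for discontinuing study drug, pregnancy among them, and continues: "Subjects who are discontinuing study drug should undergo the recommended dose taper and be monitored as clinically indicated". Section 6.1 says much the same: "Subjects who discontinue study drug should undergo the recommended dose taper and be monitored as clinically indicated". Section 6.7 repeats it with a pointer to Table 4. Footnote 1 of the schedules of assessments (Section 1.2) gives it the widest reach: "At any time during the study, subjects who discontinue study drug should undergo the recommended dose taper". Table 4, in Section 6.1, defines the taper as 100 mg "QD for 7 days, then discontinue study drug".

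**Abrupt stopping.** Sections 6.1 and 6.7 each carry a sentence that begins "If immediate or abrupt study drug discontinuation is required for an AE or medical emergency" and then calls for monitoring for hemolysis and worsening anemia. Pregnancy is not named in it.

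**How pregnancy is classified.** Section 9.4.2 opens with "Pregnancy is not reported as an AE unless" and gives two conditions: suspected interference with a contraceptive, or a complication that may qualify as an SAE. Section 6.3.3, on unblinding, names a medical emergency and a confirmed pregnancy as separate alternatives.

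**The concern.** A site with a newly pregnant subject can find two instructions that do not refer to each other. Section 9.4.2.1 says to stop immediately. Section 7.1, which names pregnancy, says that subjects who are stopping should taper. The provision that would reconcile them, abrupt stopping for an AE or medical emergency, does not clearly reach an uncomplicated pregnancy.

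The protocol treats both sides of this choice as relevant to safety. It asks for monitoring for acute hemolysis and worsening anemia when drug is stopped (6.1, 6.7, 7.1), and for counselling on possible effects on the fetus when a subject is pregnant (9.4.2.1). The situation is also foreseeable: women of childbearing potential are eligible (5.1, criterion 6), and treatment can last up to 5.6 years (4.1.4).

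**Working it through.** No alpha, power or effect size enters this point, so the check is a comparison of texts.

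| Place in the protocol | Whom it covers | Instruction | Pregnancy named? |
|---|---|---|---|
| 9.4.2.1 | Subjects who become pregnant | Immediate discontinuation; taper not mentioned | Yes |
| 7.1 | Subjects discontinuing, after a list of reasons | Recommended taper | Yes, in the list |
| 6.1 and 6.7 | Subjects who discontinue | Recommended taper | No |
| Footnote 1, schedules of assessments | Subjects who discontinue, at any time | Recommended taper | No |
| 6.1 and 6.7, abrupt-stop sentence | Subjects for whom an AE or medical emergency requires it | Monitoring; abrupt stop foreseen | No |

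**Step 1: does the general taper text reach pregnancy?** On its wording, yes. Pregnancy leads to discontinuation under 9.4.2.1 and is a listed reason in 7.1. The taper sentence there sets no reason apart.

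**Step 2: does the abrupt-stop sentence remove pregnancy from the taper?** Not clearly. The sentence needs an AE or a medical emergency. Under 9.4.2 a pregnancy is an AE only under stated conditions, and 6.3.3 distinguishes it from a medical emergency.

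**Step 3: does 9.4.2.1 settle the matter alone?** It permits two readings:

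- Dosing ends at once, and 9.4.2.1 overrides the general recommendation.
- Discontinuation begins at once, by starting the taper.

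Nothing in 9.4.2.1 chooses between them, and none of the sections compared here cross-refers to another on this point.

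**Step 4: size.** From Table 4, the taper is 7 days × one 100 mg dose per day = 700 mg. The alternative is 0 days and 0 mg. For a subject on placebo the tablets differ in the same way, but no mitapivat is involved.

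**Step 5: does the analysis break?** No. The on-treatment period ends 28 days after the end of study drug administration, including the taper (protocol 10.4.1.2; SAP 6.3.5). If D is the day of the last dose before any taper, the period ends on D + 28 without a taper, and on D + 7 + 28 = D + 35 with one. Both ends follow correctly from the actual last dose. The Safety Follow-up visit is tied to the last dose in the same way (4.1.4).

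**The case against.** **A specific, mandatory rule overrides a general recommendation.** This is the strongest reply. Section 9.4.2.1 concerns one event and says *will*; the taper text says *should* and *recommended* throughout. The list in 7.1 also includes death and loss to follow-up, where no taper can be directed, so the taper sentence cannot be meant for every listed reason. Section 7.2 likewise has a subject who withdraws consent discontinued at that time. All of this stands. It makes the override reading plausible, and 9.4.2.1 may itself be an exception to the taper, so the AE or emergency provision should not be called the only one. But the protocol does not state the override, and a site reading 7.1 with footnote 1 would have textual support for tapering.

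**The Grade 4 row of Table 7.** A reader might infer a second contradiction here. The row says "Reduce to 100 mg QD for 7 days, then discontinue study drug" for a life-threatening drug-related event, while 6.1 and 6.7 foresee abrupt stopping for an AE. The documents do not support that. The abrupt-stop sentence is conditional and can stand beside a default action. Table 7 lies within 6.7, which leaves dose modification decisions to the Investigator's clinical evaluation. Section 6.7 also refers to a Section 6.7.1.3 that the public text does not show, so one cannot say that the plan is silent on when abrupt stopping applies.

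**The analysis windows.** A reader might also infer that the ambiguity distorts the on-treatment period or the follow-up visit. Step 5 of the working shows that it does not.

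**Conclusion.** The point holds for pregnancy only. The protocol supports two courses for the same event, seven more days of dosing or none, and does not say which applies. It is a wording inconsistency with a bearing on subject safety and on consistency between sites. It is not a flaw in the statistical design: no endpoint, sample size, power or type I error figure depends on it.

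The conclusion assumes that the passages withheld from the public text contain no rule on tapering in pregnancy. It takes no position on which course is clinically right.

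**What to change.** Reconcile Section 9.4.2.1 with Sections 6.1, 6.7 and 7.1 and with footnote 1 of both schedules. One passage should state whether the taper applies when a subject becomes pregnant, and the others should refer to it. The sponsor's clinical team decides which rule applies. As an optional addition in the same edit, Table 7 could refer to the conditional abrupt-stop sentence in 6.7.

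The cost is a protocol clarification of a few lines. Neither the SAP nor any calculation needs to change, because the windows already follow the actual last dose.
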